2.8 Primary and secondary outcome measures

Primary outcome will be evaluated with the auditory hallucination subscale of the *Psychotic Symptoms Rating Scale* (PSYRATS) [68], measured at baseline assessment (T0) and post-treatment assessment (T1). This subscale comprises of 11 items evaluated by interview, which provides a detailed measure of the frequency and the quality of the hallucinations (e.g., negative content, controllability, impact, distress, etc.). The PSYRATS is the instrument that was used to evaluate the primary outcome in the trials of Leff et al. [30], Craig, Rus-Calafell [35] and our research team [4], and the most frequently used scale in CBT trials on AVH. The PSYRATS has excellent psychometric properties (see **Annex V**). Importantly, the PSYRATS measures the multiple concerns expressed by patients during the 3 focus groups performed prior to this grant application. The choice of this primary outcome best captures the multi-component complaints of the 15 schizophrenia patients that were consulted during 3 different focus groups prior to the current grant application. Indeed, during these focus groups, patients expressed concerns not only about the frequency and intensity of the voice, but also about the negative content of the utterances and the distress caused by them.

Secondary outcomes: Positive psychotic symptoms will be measured with the *Positive and Negative Syndrome Scale* (PANSS) [69]. The PANSS is one the interview scale the most often used to measure positive symptoms in clinical trials on psychological interventions in schizophrenia, and is the scale that we successfully used in our two pilot studies [4]. Quality of life will be measured with *Quality of Life Scale* (QLS) [70], that we are successfully using in our ongoing pilot trial. Enjoyment and satisfaction will also be measured using the *Quality of Life Enjoyment and Satisfaction Questionnaire - Short Form* (QLESQ-SF), a 16-item self-report scale measuring enjoyment and satisfaction experienced during the past week in various areas of daily functioning (score range from 16 to 80) [71]. Other general psychopathology measures will include measures of negative (e.g., social withdrawal) and affective symptoms, which will be assessed with the PANSS and the *Calgary Depression Sale for schizophrenia* (CDS), respectively. The CDS is a 9-item semi-structured scale to assess the level of depression in schizophrenia (score range from 0 to 27) [72]. Improvements in the beliefs about voices will be measured with the *Beliefs about Voices Questionnaire – Revised* (BAVQ-R), a 35-item self-report measure designed to assess key beliefs and responses people have concerning their voice. (score range from 0 to 105). This questionnaire includes 3 subscales: Malevolence (0-18); Omnipotence (0-18); and Benevolence (0-18) [73]. Changes in the sense of presence will be assessed using a 14-item scale, the *Change in Igroup Presence Questionnaire* (IPQ) [74]. As for **safety measures**, treatment emergent Adverse Events will additionally be collected with the *Negative Effects Questionnaire* [75]. All these instruments are available in French and in English and have excellent psychometric properties (see **Annex V**).

2.9 Outcome measurements at follow up Primary and secondary outcomes will also be measured during the follow-up visits at T2, T3 and T4 (**Fig 1**). The assessments will be identical for all time measurements.

2.10 Sample size justification In view of the large effects of AT on AVH observed by available studies [30, 35] and by our pilot data, in addition to the small to moderate effects of CBT [26] on these symptoms, we are expecting to observe a superior efficacy of AT over CBT (f , effect size for the difference on AVH is estimated at 0.25). We thus estimated with G-Power that the recruitment of 52 patients per intervention group will allow to detect superior effects (using pre- and post-therapy assessments) of AT over CBT on auditory hallucinations with a statistical power of 80% and an alpha of 0.05. To include the predicted attrition

of 20% (based on our ongoing trial) and 5 degrees of freedom to control for possible confounders, the total sample to recruit will be 68 per group ($52 \times 2 = 104$; $104 + 5 = 109$; $109 / 0,8 = 136$ total; $136 / 2 = 68$ per group).

2.11 Health service research issues: Our pilot data has been showing a greater improvement in the quality of life of patients after AT compared to CBT. We have thus included the QLS in the trial. The effect size for the difference on quality of life is estimated to be at least moderate (f , effect size of 0.25), which indicates that 68 patients per intervention group is enough to demonstrate the superiority of AT over CBT with a statistical power higher than 80% and an alpha of 0.05.

2.12 Recruitment We did presentations in various centers quarterly, resulting to the referral of at least one patient reference weekly. Since March 2017, we have been able to recruit at least 3 patients per month in the project. The recruitment of 136 schizophrenia patients with treatment resistance within 4 years is feasible (from April 2019 to January 2023) (see **Annex II** for a detailed Timeline).

2.13 Acceptability and adherence To estimate the acceptability of both interventions, we conducted a short survey on 10 patients. Patients reported that both therapies were helpful. As for AT, the initial sessions were more emotionally challenging, though as the sessions went on, they acquired more self-confidence. CBT participants, on the other hand, reported that the therapy did help to better understand their voices, however, they would lack the motivation to complete their homework (voice journal). Moreover, overall acceptability and adherence were measured based on our pilot data of 39 participants. We had an enrollment rate of 85% (i.e. patients assessed to be eligible and consented to participate) and a patient retention rate of 80% (i.e. completed the treatment), which is very similar to the rates observed in other CBT trials [42]. These observations confirm the strong acceptability of both treatments.

2.14 Follow-up rate Based on our current experience with the project, only 2 participants have not responded to their follow-up appointments. This results in a follow-up rate of 95%. In addition to scheduling assessments 2 weeks beforehand, as we are currently doing, the coordinator will give participants a courtesy-call the day before their appointment and the participants will receive a compensation at each assessment.

2.15 Centers Our research team has access to large cohorts of schizophrenia patients receiving treatment at the Mental Health University Institute of Montreal (1,500 patients) and the Philippe-Pinel Institute (300 patients). In the last 3 years, we have also established collaboration with many other clinical teams in the Montreal region (see letters of support).

2.16 Types of analyses To compare the effects of both interventions (AT and CBTp) on the primary outcome (e.g. AVH) from T0 (baseline) to T1 (end of both therapies), we will perform linear mixed-effects models (LMM) analyses [76-81]. Such analyses have been successfully used by [name] in CIHR-funded RCTs [82, 83]. The major capability of LMM is that it handles unequal variances and correlated data, which are very common in treatment trials. LMM also allows for an unequal number of repetitions. LMM procedure applies both fixed and random effects, which make it suitable for clinical trial data. LMM is based, furthermore, on maximum likelihood methods, versus the usual analysis of variance (ANOVA) methods, which require sphericity of data, and are not robust using small to moderate sample sizes. LMM thus presents a clear advantage over ANOVA methods in modeling real data. There will be a per-protocol analysis and an intention-to-treat analysis with the inclusion of withdrawals to yield a more conservative effect of treatments. Potential differences in socio-demographic variables at baseline will be considered as co-variables. The effects of both interventions on secondary outcomes from T0 to T1, as well as the effects on both interventions on primary and secondary outcomes *during the follow-up* (T2, T3 and T4) will also be assessed using linear mixed models.

2.17 Frequency of analyses A statistician will perform analyses on recruitment rates, retention rates, compliance rates and adverse events every 6 months for the safety data committee. The analysis of primary and secondary outcomes will be performed at the end of the trial.

2.18 Subgroup analyses Due to stratification, an equal number of men and women will be assigned to both treatment arms to examine the gender differences in both interventions. Our primary goal is to show the superior efficacy of AT on AVH. In our pilot data, we did not see any sex nor gender differences in this regard. We will nonetheless ensure this by completing an exploratory analysis on gender at the end of the study.

2.19 Pilot study Inspired by the study of Leff et al. [30], which used a simple laptop, we made the necessary technological improvements to offer patients a therapy with an enhanced feeling of presence and immersion. We first built a 3D therapy for a specific population of schizophrenia patients with well-defined treatment resistance and conducted a partial cross-over trial comparing AT to treatment-as-usual. In a sample of 15 patients, we showed that AT produced a large improvement in AVH, while treatment-as-usual showed no therapeutic effects. Notably, *clinical improvements remained significant at the end of the 3-month follow-up*. These results suggest that AT is a highly promising intervention for refractory AVH in schizophrenia. These findings have been published on line in *Schizophrenia Research* [4]. In addition to gathering this very promising data, we also adapted the well-known CBT developed by Birchwood and Chadwick [32] to ease future comparisons with AT. CBT was chosen as it is the best evidence-based psychological treatment for psychosis, while benefits are small to moderate [26]. Our research team secured a funding from *Otsuka Pharmaceuticals* allowing us to perform the pilot RCT comparing AT to CBT for the treatment of refractory AVH in schizophrenia. This 9-week modified CBT was administered to 16 schizophrenia patients and the intervention showed small to moderate effects on AVH that are in the *same therapeutic range* as a recent meta-analysis [26]. Preliminary results of this new trial comparing CBT (16 patients) and AT (23 patients) showed a trend toward the superiority of AT over CBT on AVH, positive symptoms of schizophrenia and quality of life. For the 3 outcomes, the difference between treatments was in the moderate range. The superior improvements attributable to AT were also present at the end of the 3-month follow-up. Recent evidence from other studies [30, 35] and our own phase-II clinical trial [4] justifies the importance of moving forward to now compare AT with another evidence-based psychotherapy (CBT) by using a more rigorous methodology. Thus, we are now requesting funding from the CIHR to do a single-blind RCT seeking to show that AT is superior to CBT for the treatment of refractory AVH in schizophrenia.

SECTION 3 – TRIAL MANAGEMENT

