Study timeline: A detailed timeline has been included in the **Annex II** for this proposed 5-year study plan.

1.5 Risks to the safety of participants The main issue with the current trial is the tolerability of the first sessions of AT. Importantly, this issue has been fixed in our prior work [41]. As the first 2 AT sessions generate strong negative emotions in patients, this can lead them to consider quitting the therapy. In the trial

from Leff et al. [30], more than 30% of patients did not complete the trial. Being aware of this issue, we have integrated support provided by the therapist between sessions from the creation of avatar to session 3 or as needed by the patients. This support was also offered to CBT participants by the therapist. Additionally, we have upgraded our VR interface to make it more user-friendly reducing the time required to create the Avatar. Due to these improvements, we were able to lower the drop-out rate to 21.1%, which is very similar to the drop-out rate observed in CBT trials [42].

SECTION 2 - THE PROPOSED TRIAL

2.1 The trial design: Single-blinded randomized-controlled, single-site parallel study of AT versus CBTp developed in accordance with the CONSORT guidelines. Patients with schizophrenia or schizoaffective disorder will be randomized to receive either AT or CBTp. Conditions for treatment delivery, duration and monitoring will be equivalent across all allocations. Both groups will begin with a baseline clinical assessment before randomization (T0). Participants will receive 9 weekly sessions of 1 hour beginning within the next week after T0. After completion of the therapies, a post-treatment clinical assessment will be performed the week after the last session (T1). Follow-ups for treatment arms will be ensured 3 months (T2), 6 months (T3) and 12 months (T4) after the post-treatment clinical assessment (T1) during which patients will receive treatment-as-usual from their treating team. No further treatment from the research team will be offered after T1 apart from their regular appointments with their psychiatrist and other professionals.

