2.3 Randomization method After completion of baseline assessment (T0), patients will be randomly assigned to a 1:1 ratio to either AT or CBTp. The sequence generation and allocation concealment will be ensured using an independent and secure Internet-based service (<https://www.sealedenvelope.com>) that conceals assignments by giving the allocation available one person at a time as the patients are enrolled. Treatment assignment will be determined by permuted block randomization with varying block sizes, which ensures that the researchers and research team members will not be able to predict the exact assignment sequence. Randomization will use cohort stratification to balance assignments according to potential confounding factors. Stratification will account for the potential confounding effects of gender and clozapine. Clozapine has a small-to-moderate superior efficacy for the treatment of refractory hallucinations in schizophrenia [20]. The inclusion of an equal ratio of men and women in each treatment arm will allow to perform exploratory analyses on potential gender differences. Importantly, 17 RCT conducted by our research team (Drs. [name], [name], [name] and [name]) on psychological, technological and pharmacological interventions, including 5 clinical trials funded by the CIHR [41, 49-64] and one recently funded trial by the CIHR ([name] 2018) have used the same methodology.

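### Section 2.16 does not say how baseline PSYRATS-AH enters the primary mixed model; a T1 contrast with a common T0 mean across arms would use T0 more efficiently if T0 means would otherwise be free by arm

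*Combined protocol and SAP*

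**What the plan says.** Section 2.16 describes the primary analysis as linear mixed-effects models "To compare the effects of both interventions (AT and CBTp) on the primary outcome (e.g. AVH) from T0 (baseline) to T1". It gives no fixed-effects formula, contrast or covariance structure. On covariates it says "Potential differences in socio-demographic variables at baseline will be considered as co-variables"; section 2.5 adds medication changes. Baseline PSYRATS-AH is mentioned in neither place as a model term. Section 2.16 also plans a per-protocol analysis and "an intention-to-treat analysis with the inclusion of withdrawals".

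The baseline score is available. Section 2.8 has the primary outcome "measured at baseline assessment (T0) and post-treatment assessment (T1"). It precedes allocation: section 2.1 says "Both groups will begin with a baseline clinical assessment before randomization (T0"), and section 2.3 says "After completion of baseline assessment (T0), patients will be randomly assigned".

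Section 2.10 states that "the recruitment of 52 patients per intervention group will allow to detect superior effects (using pre- and post-therapy assessments) of AT over CBT". It gives f = 0.25, 80% power and alpha 0.05, but no pre-post correlation, SD or named G*Power test.

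**The concern.** The wording of 2.16 fits at least two models. In one, T0 and T1 are both responses, each arm has its own T0 mean, and the treatment effect is the group-by-time interaction, that is, the difference in mean change. In the other, the effect is the T1 difference adjusted for T0, either through a common T0 mean or with T0 as a covariate.

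Under randomisation both estimate the same effect, but they can give different standard errors and p-values on the same data. Because T0 is measured before allocation, any arm difference in T0 means is chance. A model that estimates those means separately carries the chance difference into the treatment contrast; a common mean does not. What is at stake is the precision of the primary comparison, and having its contrast fixed in advance. Precision matters here: section 2.12 plans about four years to recruit 136 treatment-resistant patients, and the comparator is active.

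**Working it through.** **The plan's own figure.** The inflation in 2.10 reproduces: 52 × 2 = 104; 104 + 5 = 109; 109/0.8 = 136.25, stated as 136. The 104 can be reached only by supplying an input that 2.10 does not give. For example, a between-factors repeated-measures test at rho = 0.6 has noncentrality 104 × 0.25² × 2/(1 + 0.6) = 8.125 and power 80.6%. The same test at rho = 0.5 needs 98, and a one-sided two-group test needs 102. The group-by-time interaction test with N = 104 has 99.9% power at rho = 0.5. So 2.10 does not reveal which contrast is intended.

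**Inputs for the comparison.** From the documents: 68 randomised per arm, and T0 before randomisation. Assumed: rho 0.3 to 0.8; SD ratio k = (T1 SD)/(T0 SD) of 0.8, 1 or 1.2; and either complete data (68/68) or 68 at T0 with 54 at T1 (68 × 0.8 = 54.4).

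**Formulas.** Let s0 and s1 be the SDs, N per arm at T0 and n per arm at T1. Per-arm variance of the contrast:

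- T0 means free by arm: s1²(1 − rho²)/n + (s0 − rho·s1)²/N
- T0-adjusted (common T0 mean): s1²(1 − rho²)/n

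The extra term is a square, so in large samples it is never negative. With complete data the first line reduces to the change-score variance: s0² + s1² − 2·rho·s0·s1 = s1²(1 − rho²) + (s0 − rho·s1)².

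**Worked cell, rho = 0.5, equal SDs of 1.**

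- Complete data: free (0.75 + 0.25)/68; adjusted 0.75/68. Variance saving 25.0%; standard error 1 − √0.75 = 13% smaller.
- 68 at T0, 54 at T1: adjusted 0.75/54 = 0.01389; extra 0.25/68 = 0.00368; free 0.01757. Saving 0.00368/0.01757 = 20.9%; standard error 11% smaller.

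**Variance saving (%), large-sample formulas.**

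| k | T0/T1 per arm | rho 0.3 | 0.5 | 0.6 | 0.7 | 0.8 |
|---|---|---|---|---|---|---|
| 1 | 68/68 | 35.0 | 25.0 | 20.0 | 15.0 | 10.0 |
| 1 | 68/54 | 30.0 | 20.9 | 16.6 | 12.3 | 8.1 |
| 1.2 | 68/68 | 23.8 | 12.9 | 7.8 | 3.4 | 0.3 |
| 1.2 | 68/54 | 19.9 | 10.5 | 6.3 | 2.7 | 0.2 |
| 0.8 | 68/68 | 49.8 | 42.9 | 39.8 | 37.2 | 36.0 |
| 0.8 | 68/54 | 44.1 | 37.3 | 34.4 | 32.0 | 30.9 |

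**Cost of estimating the baseline slope.** Multiply the adjusted variance by 1 + 1/(2n − 4). With k = 1 the 68/68 row becomes 34.5, 24.4, 19.4, 14.4, 9.3 and the 68/54 row 29.3, 20.2, 15.8, 11.4, 7.2. In the worst cell (k = 1.2, rho = 0.8) the small gain becomes a loss of 0.4% (68/68) to 0.7% (68/54). A simulation with k = 1, 20,000 runs and T1 missing completely at random gave 34.3, 24.1, 19.7, 14.5, 8.9 and 30.2, 19.8, 16.9, 12.2, 7.4, in agreement.

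**The case against.** The strongest reply is that the loss is conditional. Section 2.16 gives no model formula, and its T0-to-T1 phrase may describe only the period compared. A reader might infer that the plan does leave T0 means free by arm. That is the ordinary reading of a mixed-model comparison of change, but the text does not establish it; if the statistician already constrains the T0 means, nothing is gained beyond having it written down. This stands, and the point is worded accordingly.

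Second, the size is not sourced. Rho = 0.5 has no better claim than 0.6, and the SD ratio matters as much. Enrolling only patients with persistent refractory voices could narrow the T0 spread relative to T1, which is the low-gain direction: at k = 1.2 and rho = 0.5 the saving is 11-13%. A reader might infer that some gain is assured; the grid does not support that, since its lower end is about zero. This also stands.

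Third, a mixed model might be thought to solve the problem already. Section 2.16 credits the method because "it handles unequal variances and correlated data", and the intention-to-treat analysis keeps withdrawals. Neither removes the loss. Modelling the correlation does not make the T0 means equal, and participants seen only at T0 shrink the extra term through N without removing it.

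Fourth, follow-up may be better than assumed. The 80% in 2.13 is treatment completion, so 54 assessed at T1 is only an assumption; 2.14 reports 95% follow-up. At 65 of 68 the saving at rho = 0.5 with equal SDs is (0.25/68)/(0.75/65 + 0.25/68) = 24%, so this does not weaken the point. Nor do the five degrees of freedom that 2.10 reserves for confounders. They are not itemised, so they neither include nor exclude baseline severity, though they may already cover the cost.

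**Conclusion.** The point holds as a low-cost gain in precision and pre-specification, conditional on the model otherwise leaving T0 means free by arm. Over the assumed grid the variance saving runs from about 0% to 50%. With equal SDs it is 21-25% at rho 0.5, 17-20% at rho 0.6 and 8-10% at rho 0.8, less up to about one point for slope estimation. The worst case is a loss under 1%. The algebra and the silence of 2.16 are certain; the actual gain in this trial is not, because the documents give neither rho nor SDs.

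Two stronger conclusions should not be drawn. The free-mean model is not biased or invalid: randomisation makes both contrasts estimate the same effect. And the sample size is not shown to be wrong: 52 per group depends on a test that 2.10 does not name, and it need not change.

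**What to change.** In 2.16, define the primary contrast as the AT-CBT difference in PSYRATS-AH at T1 from a linear mixed model with T0 and T1 as responses and a common T0 mean across arms. This form keeps participants who have only a T0 score in the intention-to-treat model, as 2.16 intends. Analysis of covariance on T0 is the equivalent when data are complete, but on its own it drops those participants from the analysis set.

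Use the same form for T2 to T4, and for secondary outcomes that have a pre-randomisation value. The presence questionnaire may not have one, since section 2.2 has it completed after AT sessions.

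The cost is a few lines of SAP wording, the model code and about one degree of freedom. No extra patients, visits or data are needed.

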3.1 Day to day trial management

The study coordinator will be responsible of assessing patients' eligibility, obtaining informed consents and enrolling participants in the trial. The coordinator will ascertain intervention assignment by means of an external centralized website for randomization that will be independent of the recruitment process. After the randomization process, the coordinator will contact the corresponding therapist to provide participant information. The coordinator will manage the assessments to evaluators and participants for all time-measures, the inter-rater reliability simulations, and the data handling. He or she will also document medication dosages during follow-up assessments.

The therapists will conduct the 9 weekly sessions and offer support between sessions if needed. Independent counselling psychologists will conduct treatment-integrity evaluations twice yearly based on audio-recorded sessions and grids developed to assess adherence to manualised approaches and skills in delivery.

The independent evaluators having clinical experience with psychotic patients will be masked from objectives, hypotheses and intervention allocations. Inter-rater reliability simulations will be completed every 4 months with the coordinator.

The statistician will be masked from intervention allocations. He will produce outcome analysis at the end of the study and will produce a report to the data safety committee biannually or upon request. Statistical analyses will be performed by [name], a full-time biostatistician at the Mental Health University Institute

of Montreal. He has more than 15 years of experience and he is currently involved with more than 20 researchers at the Centre for different ongoing clinical trials on psychosocial interventions.

Data handling *Data* will be stored and processed anonymously, and codes will be allocated to each patient. We will use coded software designed to store and retrieve research data, which will be converted into SPSS or EXCEL files. Data flow will be monitored on a patient-by-patient basis by the coordinator with a summary file to provide information on patients' current status.

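### Randomisation is stratified by gender and clozapine, but the primary mixed model names neither, and its imbalance-based covariate rule cannot reach clozapine and will almost never reach gender

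*Combined protocol and SAP*

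**What the plan says.** - **Randomisation (section 2.3).** Allocation is 1:1 in permuted blocks. "Stratification will account for the potential confounding effects of gender and clozapine". The reason given for clozapine concerns the symptom that the primary outcome measures: "Clozapine has a small-to-moderate superior efficacy for the treatment of refractory hallucinations in schizophrenia".
- **Primary analysis (section 2.16).** A linear mixed model compares the arms from T0 to T1. No fixed effects are listed. The one sentence on covariates is "Potential differences in socio-demographic variables at baseline will be considered as co-variables". It gives no list, no test and no threshold. Linear mixed models are also planned for the follow-up visits, again with no covariates named.
- **Gender (section 2.18).** Because of stratification, the plan expects that "an equal number of men and women will be assigned to both treatment arms". Gender otherwise gets only an exploratory analysis.
- **Sample size (section 2.10).** The calculation adds "5 degrees of freedom to control for possible confounders" without saying which confounders are meant.
- **Medication (section 2.5).** The promise to control for medication concerns changes in treatment. It does not cover clozapine status at baseline.

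**The concern.** When randomisation is stratified, the arms are more alike on the strata than chance alone would make them. If the strata predict the outcome, a model that omits them leaves their variance in the residual. The standard error is then too large, the test is conservative and the interval is too wide.

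The plan treats two variables as important enough to stratify on, then states a covariate rule that passes over both. The rule also responds to observed imbalance. In a randomised trial, imbalance says nothing about whether a variable is worth adjusting for; its relation to the outcome does. A rule of this kind leaves the primary model undetermined until the arms have been compared at baseline.

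**Working it through.** **The plan's own figure.** (2 × 52 + 5) / (1 − 0.20) = 109 / 0.8 = 136.25, which agrees with the stated 136. The 52 per group needs something the plan does not state. With f = 0.25 (d = 0.5), a two-sided t test on 104 patients has 71.4% power. An analysis of T1 adjusted for T0 reaches 80.7% on 104 if the T0–T1 correlation is 0.45. The point made here does not depend on that figure.

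**Can the rule admit the strata?** Clozapine use is a treatment variable, so the wording excludes it. For gender, stratified blocks were simulated for 136 patients (3,000 runs per setting; block sizes 2/4, 4/6 or 4/6/8; 25% or 50% in one gender; 40% on clozapine; all assumed). A chi-square test at p < 0.05 flagged gender in 0% of trials at randomisation, and in at most 0.03% after 20% random dropout.

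**Cost of leaving out the strata.**
- From section 2.10: f = 0.25, read as d = 0.5 at T1; alpha 0.05, taken as two-sided; 136 × 0.8 = 108.8, taken as 54 per arm.
- Assumed: T0–T1 correlation ρ = 0.5 (range 0.3 to 0.7); the strata explain a share r = 0 to 10% of the residual variance.
- T1 adjusted for T0: residual SD = √(1 − ρ²) = 0.866, and SE = 0.866 × √(2/54) = 0.1667. The noncentrality at r = 0 is 0.5 / 0.1667 = 3.00.
- Stratified blocks shrink the true SE by √(1 − r) whether or not the model contains the strata. With the strata in, the estimated SE shrinks too. With them out it does not, so the effective critical value is t / √(1 − r).
- At r = 10%: noncentrality 3.00 / √0.90 = 3.16; critical value 1.983 with the strata in and 1.983 / √0.90 = 2.090 with them out.

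| r | Power, strata out | Power, strata in | Type I error, out | Interval wider by 1/√(1 − r) − 1 |
|---|---|---|---|---|
| 0 | 84.4% | 84.4% | 5.0% | 0% |
| 5% | 85.0% | 86.2% | 4.4% | 2.6% |
| 10% | 85.7% | 88.0% | 3.9% | 5.4% |

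At r = 10%, power out and in is 78.2% and 81.2% for ρ = 0.3, and 95.8% and 96.7% for ρ = 0.7.

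**Change from T0 to T1 as the contrast.** SD = √(2(1 − ρ)) = 1 at ρ = 0.5. Power out and in is 73.1% and 73.0% if the strata do not predict change, 73.6% and 75.2% if they explain 5% of its variance, and 74.1% and 77.4% at 10%.

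**Simulation check.** 8,000 trials, N = 136, blocks of 4 and 6, 70% men, 40% on clozapine, 20% random dropout (all but N and the dropout rate assumed), with T1 adjusted for T0. Power out and in was 83.9% and 83.6% at r = 0, 84.2% and 85.2% at 5%, and 84.5% and 87.2% at 10%. Type I error with the strata out was 5.1%, 4.6% and 4.0%.

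**The imbalance rule.** Suppose five independent covariates are screened. The chance that at least one enters is 1 − 0.95⁵ = 22.6% at p < 0.05, or 1 − 0.90⁵ = 41.0% at p < 0.10. In 20,000 simulated trials per setting, type I error stayed between 4.6% and 5.1%. If the covariates explain 10% of the variance, power is about 84% screened, 84% unadjusted and 86% with all five named. If they explain nothing, naming all five gives 82% against 83% screened.

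**The case against.** - **Adjustment may already be intended.** Section 2.10 budgets degrees of freedom for confounders, and section 2.3 describes gender and clozapine in those terms. This is the natural reading, but no sentence links the two, and section 2.16 states a different rule.
- **The covariate sentence has no threshold, so gender could still be included by discretion.** True. That confirms that the covariate set is open.
- **Clozapine may predict severity without predicting change during therapy.** Section 2.5 asks for stable medication from T0 to T1, so a shift that is equal at both visits is plausible. With a simulated shift of 0.5 SD, power out and in was 72.8% and 72.4% for change, and 83.4% and 83.8% for T1 adjusted for T0. In that case nothing material is gained. This objection stands and sets the lower end of the range.
- **Masking guards against misuse.** Section 3.1 says "The statistician will be masked from intervention allocations". This limits steering towards one arm but does not fix the covariates.
- **How T0 enters the model matters more than the strata.** At ρ = 0.5 it moves power from about 84% to 73%. That is correct, and it is a separate gap; the fix below is worded to work under either form.

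**Conclusion.** The concern holds, with modest consequences. The primary model does not reflect the stratified randomisation, and its stated covariate rule works against including either stratum. Omission causes no bias and no excess of false positives. At ρ = 0.5 with T1 adjusted for T0, it costs 0 to 2 points of power (0 to 3 at ρ = 0.3, 0 to 1 at ρ = 0.7), and about 3 points at most for the change contrast at ρ = 0.5. The imbalance rule gains nothing over no adjustment when the covariates are prognostic.

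These figures rest on an assumed correlation and on the strata explaining 0 to 10% of residual variance; the documents support neither number directly. Larger assumed effects (0.5 residual SD for gender and 0.8 for clozapine, N = 104) widened the gap to about 6 points, 74.4% against 80.6%. If the strata predict nothing, the gain is zero.

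**What to change.** Replace the covariate sentence in section 2.16 with text to this effect:

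> The primary T0–T1 model includes gender and baseline clozapine use, the two randomisation strata, as pre-specified covariates. They enter so that they adjust the treatment contrast: as covariates if T1 is the outcome with baseline adjustment, or with stratum-by-time terms if T0 is part of the outcome. Any further covariates are named in advance on prognostic grounds. None is selected by comparing the arms at baseline.

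Use the same strata in the T0–T4 models, and state that the 5 budgeted degrees of freedom apply only to the primary T0–T1 model.

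**Cost.** A few sentences, no new data, and N unchanged at 136. In the primary model the strata use 2 degrees of freedom when T1 is the outcome (3 with baseline), or 2 + 2 = 4 with stratum-by-time terms. That leaves 1 to 3 of the 5. Over T0–T4, full stratum-by-time terms use 2 + 2 × 4 = 10, outside that budget. If the strata predict nothing, closed-form power is essentially unchanged (84.4% either way with baseline adjustment; 73.1% against 73.0% for change). The largest loss seen in that case by simulation was 0.3 points.
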